3.3 Study periods

The study is comprised of the following periods:

- **Screening Period (Day -28 to Day -1)**

Patients diagnosed with treatment-naïve or steroid refractory aGvHD will have screening activities and assessment of inclusion and exclusion criteria once the study informed consent is obtained. Upon confirmation of eligibility, the patients will be enrolled to the study.

- **Treatment Period (Day 1 to Week 24)**

Study treatment will begin on Day 1. Subjects meeting eligibility requirements will be treated with ruxolitinib plus corticosteroids +/- CNI for 24 weeks (approximately 6 months) unless discontinuation criteria (See [Section 9.1.1](#)) or withdrawal from the study for other reasons occurs. Dose modifications are allowed for safety. Patients that have not discontinued ruxolitinib by the end of Week 24 or experience aGvHD flare may continue to receive treatment for a maximum of 48 weeks (See [Section 6](#) for treatment details and dose modifications). In this case, the end of treatment for such patients will extend beyond Week 24 but MUST end by Week 48.

Study visits will occur per the following schedule to monitor tolerability and efficacy of the study treatments during the Treatment period:

- Weekly visits from Day 1 up to Day 56;
- Visits every 4 weeks beyond Day 56 and until Week 24 or End of Treatment (EOT), whichever occurs later.

A 30-day safety follow-up visit will be done for all patients after the last dose of ruxolitinib.

- **Long-term follow-up Period (From EOT to Month 24)**

[figure not shown]
Recognizing that aGvHD is a complication of alloSCT that often leads to death within 2 years after the procedure, and that assessment of long-term safety and durable efficacy is clinically meaningful, all patients (responders and non-responders in both arms, regardless of when treatment was discontinued) will be followed to collect long term data including: survival, any relapse/progression of the underlying hematologic disease for which the alloSCT procedure was performed (refer to [Section 16.3](#) Appendix 3), NRM, any occurrence of graft failure, EFS, any occurrence of cGvHD, and occurrence of any second primary malignancies.

Visits will be performed at 12, 18, and 24 months from the start of treatment (Day 1).

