Patients who discontinue from study or withdraw their consent/oppose the use of their data/biological samples should be scheduled for a final evaluation visit if they agree, as soon as possible, at which time all of the assessments listed for the final visit will be performed. At this final visit, all dispensed investigational product should be reconciled, and the adverse event and concomitant medications not previously reported must be recorded on the CRF. As per [Section 4.6](#), during a Public Health emergency as declared by Local or Regional authorities i.e. pandemic, epidemic or natural disaster that limits or prevents on-site study visits, alternative methods of providing continuing care may be implemented by the investigator as the situation dictates.

Table 8-1 Assessment Schedule

Period	Screening	Treatment ¹					Safety Follow-up	Long Term Follow-up ²		
Visit Name	Screening	Day 1	Week 1-Week 8 (Weekly)	Week 12-Week 24 (Monthly)	Week 28-Week 48 (only in the case of taper or aGvHD flare, monthly)	EOT (Week 24/Week 48) ³	Safety Follow-up visit	Month 12	Month 18	Month 24
Weeks	-4	1	1 to 8	12 to 24	28 to 48	48	0	53	78	105
Days	-28 to -1	1	7 to 56	84 to 168	196 to 336	-	Last dose [contact]
Study Informed Consent/Assent	X									
Inclusion / Exclusion criteria	X									
Disease history (alloSCT and aGvHD history, CIBMTR risk assessment)	X									
HCT-Specific Co-Morbidity Index Score	X									
Demography	X									
Other relevant Medical History	X									
Prior/Concomitant Medications	X (From screening until safety follow up)									
IWRS/IRT (Registration, EOT)	X	X	X (Monthly)	X	X	X				
Physical Examination	S	S	S	S	S	S				
Body Height	X	X		X (Week 24)		X		X	X	X
Body Weight	X	X	X	X	X	X		X	X	X
Vital Signs	X	X	X	X	X	X				
Hematology	X	X	X	X	X	X				
Chemistry	X	X	X	X	X	X				

Period	Screening	Treatment ¹					Safety Follow-up	Long Term Follow-up ²		
Visit Name	Screening	Day 1	Week 1- Week 8 (Weekly)	Week 12- Week 24 (Monthly)	Week 28- Week 48 (only in the case of taper or aGvHD flare, monthly)	EOT (Week 24/Week 48) ³	Safety Follow-up visit	Month 12	Month 18	Month 24
Weeks	-4	1	1 to 8	12 to 24	28 to 48	48	0	53	78	105
Days	-28 to -1	1	7 to 56	84 to 168	196 to 336	-	Last dose [contact]
Coagulation	X	X	X	X	X	X				
Hepatitis viral serology testing (HBV, HCV)	X									
Hepatitis viral load (HBV, HCV)	X	X (Every 6 months while on ruxolitinib treatment)								
Urinalysis	X	X	X	X	X	X				
Pregnancy test (serum)	S ⁵					S ⁵	S ⁵			

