12.5 Analysis of secondary endpoints

12.5.1 Efficacy and/or Pharmacodynamic endpoint(s)

The main secondary objective of the study is to estimate the proportions of all patients who achieve a complete response (CR) or partial response (PR) at Day 28 and maintain a CR or PR at Day 56. A patient will not be considered a durable responder at Day 56 if any of the following events occurs prior to or at Day 56:

- No CR or PR at Day 28 or at Day 56.
- aGvHD progression or additional systemic therapy for aGvHD

The durable response rates for ORR at Day 56 will be estimated with 90% confidence intervals on EES. Summary statistics (frequencies and percentages). The confidence intervals will be calculated based on the exact method for binomial distribution.

All secondary efficacy endpoint analyses will be analyzed using the EES.

- Overall Response Rate at Day 14, will be derived in the same way as the primary variable ORR at Day 28.
- Duration of response (DOR)

Duration of response will be calculated for patients whose overall response at Day 28 is CR or PR according to updated standard criteria ([Harris et al 2016](#)). The start date is the date of first documented response of CR or PR (i.e., the start date of response), and the end date is defined as the date of progression or the date of addition of systemic therapies for aGvHD, since this constitutes a non-response.

Death without prior observation of aGvHD progression and onset of chronic GvHD are considered to be competing risks.

Duration of response will be censored at the last response assessment prior to or at the analysis cut-off date, if no events/competing risk occurred before or at of cut-off date.

DOR will be listed and summarized for all patients on the EES with overall response of CR or PR at Day 28.

- Overall survival (OS)

Overall survival is defined as the time from date of the start of study treatment to date of death due to any cause. If a patient is not known to have died, then OS will be censored at the latest date the patient was known to be alive (on or before the cut-off date).

The OS distribution will be estimated using the Kaplan-Meier method, and the Kaplan-Meier curves, medians, 1, 2, 6, 12, 18 and 24 month survival estimates and 95% confidence intervals will be presented.

- Event Free Survival (EFS)

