Week 32	Study Day 224	Study Days 211 – 238
Week 36	Study Day 252	Study Days 239 – 266
Week 40	Study Day 280	Study Days 267 – 294
Week 44	Study Day 308	Study Days 295 – 322
Week 48	Study Day 336	Study Days 323 – 350
Month 12*	Study Day 365	Study Days 351 – 455
Month 18*	Study Day 546	Study Days 456 - 636
Month 24*	Study Day 730	Study Days 637 - 820

Study Day 1 = start date of study treatment;

EOT assessments are mapped to the time points as appropriate;

Last contact date

The last contact date will be derived for patients not known to have died at the analysis cutoff using the last complete date among the following:

Table 3-2 Last contact date data sources

Source data	Conditions
Last contact date/last date patient was known to be alive from Survival Follow-up page	Patient status is reported to be alive, lost to follow-up or unknown.
Start/End dates from new aGVHD treatment since discontinuation from study treatment	Non-missing medication/procedure term.
Start/End dates from drug administration/concomitant medication record	Non-missing dose. Doses of 0 are allowed.
Disposition event date from the disposition log page	No condition.

Source data	Conditions
- aGvHD assessment date - any specific efficacy assessment date if available (e.g., cGvHD assessment, graft failure assessment, second primary malignancy assessment, hematologic disease relapse/progression assessment)	Non-missing assessment
Laboratory/PK collection dates/ [REDACTED] [REDACTED]	Sample collection marked as 'done'.
Vital signs date	At least one non-missing parameter value
Collection date of acceptability and palatability questionnaire	Assessment performed is "Yes" [REDACTED]
Start/End dates of AE	Non-missing verbatim term

The last contact date is defined as the latest complete date from the above list on or before the data cutoff date. The cutoff date will not be used for last contact date, unless the patient was seen or contacted on that date. No date post cutoff date will be used. Completely imputed dates (e.g. the analysis cut-off date programmatically imputed to replace the missing end date of a dose administration record) will not be used to derive the last contact date. Partial date imputation is allowed for event (death)/censoring coming from 'Survival information' eCRF.

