3.7 Analysis of secondary efficacy objective(s)

3.7.1 Secondary endpoints

- **Overall Response Rate at Day 14**

Overall Response Rate at Day 14 is defined as the proportion of patients with complete response (CR) or partial response (PR) at Day 14 according to standard criteria [\[Harris 2016\]](#).

- **Duration of response (DOR)**

Duration of response will be calculated for patients whose overall response at Day 28 is CR or PR according to updated standard criteria [\(Harris et al 2016\)](#). The start date is the date of first documented response of CR or PR (i.e., the start date of response), which could be prior to or at Day 28. If it's prior to Day 28, there should not be progression or addition of systemic therapies for aGvHD between the start date of response and Day 28. The end date is defined as the date of progression or the date of addition of systemic therapies for aGvHD on or after Day 28, since this constitutes a non-response. The date of progression will be the earliest date of PD recorded in the aGvHD assessment CRF page or the date of death due to aGvHD in the death CRF page.

Death without prior observation of aGvHD progression (i.e. date of death due to non aGVHD reason (Other) in the death CRF page) and onset of chronic GvHD are considered to be competing risks.

Duration of response will be censored at the last response assessment prior to or at the analysis cut-off date, if no events/competing risk occurred before or at of cut-off date.

- **Best Overall Response**

Best overall response (BOR) is defined as proportion of patients who achieved overall response (CR or PR) at any time point up to and including Day 28 and before the start of additional systemic therapy for aGvHD.

An additional analysis will include BOR at any time point up to the data cut-off date and before the start of additional systemic therapy for aGvHD. A swimmer plot for overall response by age group, SR-aGvHD vs Treatment Naive and formulation will also be provided for all treated subjects.

- **Overall survival (OS)**

Overall survival is defined as the time from date of the start of study treatment to date of death due to any cause. If a patient is not known to have died, then OS will be censored at the latest date the patient was known to be alive (last contact date on or before the cut-off date).

- **Event Free Survival (EFS)**

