Event-free survival is defined as the time from the study treatment start date to the date of hematologic disease relapse/progression, graft failure or death due to any cause. If a patient is not known to have any event, then EFS will be censored at the latest date the patient was known to be alive (last contact date on or before the cut-off date).

- **Failure Free Survival (FFS)**

Failure-free survival is defined as the time from the study treatment start date to date of hematologic disease relapse/progression, non-relapse mortality (NRM) or addition of new systemic aGvHD treatment. Each type of failure as a competing risk for the other two, and onset of chronic GvHD is considered as a competing risk for all three types of failure. If a patient is not known to have any event or competing risk, then FFS will be censored at the latest date the patient was known to be alive (last contact date on or before the cut-off date).

- **Non-relapse mortality (NRM)**

Non-relapse mortality is defined as the time from the study treatment start date to date of death not preceded by hematologic disease relapse/progression. Hematologic disease relapse/progression is considered a competing risk for NRM with the date of hematologic disease relapse/progression being the earlier of documented hematologic disease relapse/progression or institution of therapy to treat potential hematologic disease relapse/progression. If a patient is not known to have died or to have relapsed/progressed, then NRM will be censored at the latest date the patient was known to be alive (last contact date on or before the cut-off date).

- **Incidence of Malignancy Relapse/Progression (MR)**

Malignancy relapse/progression is defined as the time from the study treatment start date to date of hematologic malignancy relapse/progression. Deaths not preceded by hematologic

malignancy relapse/progression are competing risks. If a patient is not known to have event or competing risks, then MR will be censored at the latest date the patient was known to be alive (last contact date on or before the cut-off date).

- **Cumulative steroid dosing until Day 56**

The weekly cumulative steroid dose will be calculated for each patient up to Day 56 and the overall cumulative steroid dose will be calculated for each patient at Day 56. In addition, the proportion of patients with any dose reduction and any dose reduction of at least 50% in corticosteroids from baseline until EOT will be provided.

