3.7.2 Statistical hypothesis, model, and method of analysis

All secondary efficacy endpoint analyses will be analyzed using the EES.

- **Overall Response Rate at Day 14**

Overall response rate at Day 14 will be calculated based on the local investigators review of aGvHD assessment data. They will be summarized using descriptive statistics (N, %) with two-sided exact binomial 90% CIs [Clopper and Pearson 1934].

- **Best Overall Response (BOR)**

BOR up to and including Day 28 will be calculated based on the local investigators review of aGvHD assessment data. They will be summarized using descriptive statistics (N, %) with two-sided exact binomial 90% CIs [Clopper and Pearson 1934]. BOR up to cut-off date will also be analysed in the same way.

- **Duration of response (DOR)**

The estimated cumulative incidence rates and 95% confidence intervals at 1, 2, 6, 12, 18 and 24 months will be presented. The cumulative incidence curve will be plotted. DOR will be summarized for all patients in the EES with overall response of CR or PR at Day 28.

- **Overall survival (OS)**

The OS distribution will be estimated using the Kaplan-Meier method, and the Kaplan-Meier curves, medians, 1, 2, 6, 12, 18 and 24 month survival estimates and 95% confidence intervals [Brookmeyer and Crowley 1982] will be presented.

- **Event Free Survival (EFS)**

The EFS distribution will be estimated using the Kaplan-Meier method, and the Kaplan-Meier curves, medians, 1, 2, 6, 12, 18 and 24 month survival estimates and 95% confidence intervals [Brookmeyer and Crowley 1982] will be presented.

- **Failure Free Survival (FFS)**

Cumulative incidence curve for FFS as well as estimates at 1, 2, 6, 12, 18 and 24 months with 95% confidence intervals will be presented, accounting for onset of chronic GvHD as the competing risk.

In addition, the cumulative incidence of each of the three components considering the other two components as a competing risks will be estimated. Onset of chronic GvHD is considered as a competing risk for all three types of failure.

- **Non-relapse mortality (NRM)**

The cumulative incidence curve for NRM as well as estimates at 1, 2, 6, 12, 18 and 24 months with 95% confidence intervals will be presented.

- **Incidence of Malignancy Relapse/Progression (MR)**

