6.4.3 Definition of new or additional systemic treatment for aGvHD

The data source to search for the new or additional systemic therapy is the CRF of “Prior and Concomitant Medication” (CONMED) or CRF “Prior or Concomitant non-drug therapies/procedures” and “Study treatment CNI”.

Systemic therapies are identified using the Route (if CMROUTE is Intramuscular, Intravenous, Oral, Subcutaneous, or Parenteral).

Any of the following therapies represent new or additional systemic therapy for aGvHD:

- Any CNI therapy being initiated newly as ‘treatment for aGvHD’ after the baseline (as recorded on Study treatment CNI and with indication = “treatment for aGvHD” on CONMED page). That means when a subject starts a new systemic therapy during study treatment for the indication ‘treatment for aGvHD’, or a subject received the same therapy before as prophylaxis and then changed to treatment of aGvHD as indication, this will be considered as new or additional systemic treatment.

CNI therapy given as ‘treatment for aGvHD’ that started after Day 1 will be considered as new or additional systemic treatment, even if the same therapy was given as treatment for aGvHD already before start of study treatment but the patient was not receiving such therapy on Day 1. Whereas a stop of such therapy after Day 1 and later re-start of the same therapy will not be considered as new or additional therapy.

Change of the drug within the defined group of CNIs or only change of the dose is not considered as new CNI treatment.

- Any other systemic treatments (excluding CNI and steroids) being initiated newly as ‘treatment for aGvHD’ or after the baseline and documented in CONMED (according to the same definitions as for CNI treatments above).
- Any other non-drug therapy/procedure being initiated newly as ‘treatment for aGvHD’ after the baseline (according to the same definitions as for CNI above) and documented on concomitant non-drug therapies/procedures (e.g. ECP).

Changes in the systemic corticosteroid therapy (captured on study treatment eCRF), e.g. change of the drug, the dose or any interruption and re-start, will not be taken into account for identification of new or additional systemic therapy, nor will any other corticosteroid therapy (in CONMED) be considered.

7 Reference

1. Anderson JR, Cain KC and Gelber RD (1983). Analysis of survival by tumor response. *Journal of Clinical Oncology*, 1(11), 710-719.

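### Duration of response is censored at the last aGvHD assessment only for patients with no later event, so the 12, 18 and 24 month estimates rest on patients selected by their outcome

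*SAP*

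**What the plan says.** SAP 3.7.1 starts DOR at the first documented CR or PR in patients who respond at Day 28. Loss of response is progression (including death from aGvHD) or added systemic aGvHD therapy. Other deaths and onset of chronic GvHD (cGvHD) are competing risks. On censoring it says "Duration of response will be censored at the last response assessment prior to or at the analysis cut-off date", under a condition that Protocol 12.5.1 shares: "if no events/competing risk occurred before or at of cut-off date". SAP 3.7.2 adds: "The estimated cumulative incidence rates and 95% confidence intervals at 1, 2, 6, 12, 18 and 24 months will be presented".

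Protocol 8.4.1.2 and Table 8-1 schedule aGvHD response weekly to Week 8, then every 28 days during treatment and at EOT. Protocol 3.3 sets the end of treatment at Week 24, or Week 48 at the latest. Table 8-1 has no aGvHD response entry at Months 12, 18 or 24. In long-term follow-up, patients "will be followed to collect long term data including: survival"; the list goes on to cGvHD but does not name aGvHD response.

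Other time-to-event endpoints are handled differently. For failure-free survival (FFS), "then FFS will be censored at the latest date the patient was known to be alive"; OS, EFS, NRM, malignancy relapse and cGvHD follow the same pattern.

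The source of late new aGvHD therapy is not settled. Table 8-1 collects concomitant medication only to safety follow-up. SAP 6.4.3 says "The data source to search for the new or additional systemic therapy is the CRF of" prior and concomitant medication, plus the non-drug therapy and CNI pages. SAP Table 3-2 lists a further source that 6.4.3 does not name: "Start/End dates from new aGVHD treatment since discontinuation from study treatment".

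**The concern.** Whether a patient leaves the risk set at the last assessment depends on what happens to that patient afterwards. A responder who stays well leaves at about Week 24 or Week 48. A responder who develops cGvHD at Month 18 stays at risk until Month 18, although response was no longer being assessed. That is informative censoring built into the rule.

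The denominators after end of treatment shrink to patients already known to have an event or competing risk. Each recorded loss is then divided by a handful of patients instead of by all who were still in response. With about 33 to 36 responders, one or two late events can decide the published 12, 18 and 24 month figures and their confidence intervals.

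**Working it through.** **Starting figure.** The documents give no precision or bias figure for DOR. The responder count comes from SAP Table 4-1: 33 of 45, with probability 0.901 and 90% CI 0.604 to 0.838. Recomputed: 0.9005 and the same limits.

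**Longest DOR for an event-free responder on scheduled visits.** Using the SAP month of 30.4375 days:
- Target days, first response Day 7, last assessment Day 336: (336 - 7)/30.4375 = 10.8 months.
- Window edges, Day 4 to Day 350: (350 - 4)/30.4375 = 11.4 months.
- Treatment ending at Week 24: (168 - 7)/30.4375 = 5.3 months, so such a patient leaves even before the 6-month point.

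This step needs no assumed rates.

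**Worked case (event counts and times assumed).** There are 33 responders. Before Week 24 there are 3 losses and 4 competing events. Eight later events fall at Months 7, 8.5, 10, 12, 14, 16, 19 and 22. Of 18 event-free patients, 14 are last assessed at 5.5 months and 4 at 11 months. The estimator is Aalen-Johansen.
- Early loss is 3/33 = 0.091, and the proportion still in response is 26/33 = 0.788.
- After the 14 are censored, 12 remain. Each event at Months 7-10 adds 0.788/12 = 0.066.
- After three such events the proportion in response is 0.788 x 9/12 = 0.591. Censoring the other 4 leaves 5 at risk, none of them event-free. Each event at Months 12-22 adds 0.591/5 = 0.118.
- With event-free patients kept to 24 months, each event adds 1/33 = 0.030.

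Loss at 24 months:
- One recorded late loss: 0.091 + 0.066 = 0.157, or 0.091 + 0.118 = 0.209, against 4/33 = 0.121.
- Two recorded: from 0.091 + 2 x 0.066 = 0.222 to 0.091 + 2 x 0.118 = 0.327, against 5/33 = 0.152.
- All eight competing: 0.091 under either rule.
- One late loss that goes unrecorded: 0.091 under either rule, against a true 0.121.

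**Second case.** Take 36 responders (80% of 45) with 4 early losses, 4 early and 6 late competing events, 21 event-free, and one recorded loss at Month 14. Under the plan the proportion still in response at 12 months is 1 - 0.111 - 0.265 = 0.624, with 5 at risk. The loss adds 0.624/5 = 12.5 points, giving 23.6%. With event-free patients followed to 24 months it adds 1/36 = 2.8 points, giving 13.9%.

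**Simulation.** It used 400,000 responders. Assumptions: loss 10% by 6 months, then a quarter of that hazard; cGvHD 30% and other death 15% by 24 months; last assessment at 5.3 months (75%) or 10.8 months (25%). The 10% matches the 6-month figure that Protocol 1.1.2.1.2 cites from the randomised phase III trial in steroid-refractory acute GvHD. True loss at 23.5 months is 14.2%.

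| Late losses recorded | Plan | Last-contact censoring |
|---|---|---|
| none | 9.7% | 9.0% |
| 25% | 13.4% | 10.3% |
| 50% | 16.8% | 11.6% |
| all | 22.9% | 14.2% |

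At 6 months the plan gives 8.9-10.2% against a true 9.4%. A common fixed day at 5.3 months gives 8.4%, equal to the true value there.

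**Reach of a Day 168 horizon.** First response falls on Days 4-31 (Week 1 to Week 4 windows), so Day 168 lies (168 - 31)/30.4375 = 4.5 to (168 - 4)/30.4375 = 5.4 months later. Four months from first response falls at the latest on Day 31 + 4 x 30.4375 = 152.75, about Day 153.

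**The case against.** The strongest reply is that the obvious repair, last-contact censoring as for FFS, is not clearly better. In the table its error exceeds the plan's when none or 25% of late losses are recorded (-5.2 against -4.5 points; -3.9 against -0.8) and equals it in size at 50% (-2.6 against +2.6). It assumes response persists where nobody is scheduled to assess it. It also barely reaches the last time point: from first response on Day 28 or Day 7 to Day 730 is (730 - 28)/30.4375 = 23.1 to (730 - 7)/30.4375 = 23.8 months. This stands, and last contact should not be the main repair. It does not rescue the plan, whose closeness at 25% comes from two offsetting errors.

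A reader might infer that every late loss is inflated, or that the DOR curve always overstates loss. Neither follows. If event-free patients drop out between late events, a very late loss can weigh slightly less than under last-contact censoring. If few late losses are recorded, the curve is too low. Unscheduled assessments that change management are also recorded (Protocol 8.3), so the 11-month limit holds for scheduled visits only. The Month 12, 18 and 24 windows in SAP 3.1.1 do not lift it, because Table 8-1 schedules no response assessment there.

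A reader might also look at the competing-risk side. If all eight late events in the worked case compete, their incidence at 12/18/24 months is 44/67/91% against 24/30/36%. SAP 3.7.2 does not say that this will be reported, so those figures should not set the severity.

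Finally, an exact 95% interval for 4/33 is 3-28%, so a shift to 16-21% lies within sampling error. DOR is also listed by patient, and a swimmer plot is planned. These points limit the harm, but they do not correct an estimate computed on an outcome-selected risk set.

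**Conclusion.** The censoring rule is wrong for the late time points. From the documents alone, on scheduled visits everyone at risk at 12 months or later has a later event or competing risk. The size rests on assumed rates and on how many late losses are recorded: 16-21% against 12% with one recorded and 22-33% against 15% with two, and no change to the loss curve in the worked case with none. The net direction for the whole curve is not fixed. The 1 and 2 month estimates are unaffected and the 6 month estimate only slightly.

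The plan should be changed, but the severity is modest. DOR is descriptive, no hypothesis is tested, and the documents do not support extending the concern to ORR at Day 28, durable ORR at Day 56 or FFS.

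**What to change.** Use one common horizon for all responders, for example Study Day 168. Count every event and competing risk up to that day, and censor event-free patients on that day or at last contact if earlier. Report DOR at 1, 2 and 4 months and drop the 6, 12, 18 and 24 month estimates as DOR. Table 8-1 (note 3) keeps patients who stop treatment early on the visit schedule to Week 24, so assessments cover the horizon. Visits in the Week 24 window after Day 168 would not count, but this does not touch the 4-month figure. Do not truncate at each patient's own last assessment, because deaths and therapy starts between visits would be lost.

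If late figures are still wanted, show them only as a supplementary analysis of recorded loss of response, censored at last contact. State there that response is not scheduled for assessment after EOT, that late losses may be missed so loss tends to be understated (9% against 12% in the worked case), and that follow-up barely reaches 24 months from first response. Name the CRF page that supplies late new aGvHD therapy, reconcile SAP Table 3-2 with 6.4.3, and say which cumulative incidences are reported.

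The cost is SAP wording and code, with no new data. The change departs from Protocol 12.5.1 and belongs in SAP section 5, which now declares none. The 6 to 24 month DOR figures are given up.
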